### **8.1.7 The Clinical COPD Questionnaire (CCQ) (Part 2 only)**

The Clinical COPD Questionnaire (CCQ) is a validated, self-administered 10-item questionnaire which measures health status and can be used to assess health-related quality of life (van der Molen et al, 2003). It has three domains: symptoms (4 items), functional status (4 items) and mental state (2 items), graded on a 7-point Likert scale from 0 to 6 (0 = no impairment). The final score is the sum of all items divided by 10; separate scores for all three domains can be calculated. Higher scores indicate a worse health status.

### **8.1.8 Instructions to participants (Part 2 only)**

Participants who satisfactorily tolerate the test dose in Part 2, or are not required to take the test dose (subject to DMC recommendations), will be trained in preparation, administration and transport of the drug product, and the care and cleaning of the nebuliser.

### **8.1.9 AE/SAE**

Any Adverse Events observed during the visit should be recorded in the eCRF.

The Investigator and any qualified designees are responsible for detecting, documenting, and reporting events that meet the definition of an AE or SAE and remain responsible for following up until the AE has resolved, has stabilised or is otherwise explained, is no longer of clinical concern, or the patient is lost to follow-up

## **8.2 Dormant period**

During the dormant period, the participants will receive monthly follow-up calls to remind them to contact the study team if they start experiencing exacerbation symptoms.

### 8.3 Pre-treatment appointment

A participant who experiences symptoms for at least [REDACTED] should contact the study team as soon as practicable to allow a remote study appointment to be undertaken within [REDACTED]

Any changes to medical history or medications reported by the patient should be recorded in the eCRE.

## 8.5 Post-treatment Follow-up calls

For all participants enrolled into the treatment period, follow-up calls will be conducted [REDACTED] [REDACTED] to discuss any AEs, changes to medications or medical history (including COVID-19 test results, if available).

Symptoms, AEs, and changes to medications or medical history (including COVID-19 test results, if available) will be recorded in eCRF.

The [REDACTED] follow-up call will be the end of study for participants enrolled into the treatment period, unless there are any unresolved AEs which should be followed up until resolved, stabilised or otherwise explained, no longer of clinical concern, or the patient is lost to follow-up [REDACTED]

## 8.6 Early Withdrawal

At the time of discontinuing from the study, if possible, an early discontinuation assessment should be conducted, as shown in the SoA (Table 8-1). [REDACTED]

[REDACTED]

• [REDACTED]

| [REDACTED]  
[REDACTED]

| [REDACTED]  
[REDACTED]

| [REDACTED]  
[REDACTED]

## 9 Pharmacovigilance

Further details are provided in Appendix 1: Adverse Events: Definitions and Procedures for Recording, Evaluating, Follow-up, and Reporting.

### 9.1 Adverse Events and Serious Adverse Events

The definitions of AEs and SAEs can be found in Appendix 1: Adverse Events: Definitions and Procedures for Recording, Evaluating, Follow-up, and Reporting.

Adverse events will be reported by the participant (or, when appropriate, by a caregiver, surrogate, or the participant's legally authorised representative).

The Investigator and any qualified designees are responsible for detecting, documenting, and reporting events that meet the definition of an AE or SAE and remain responsible for following up until the AE has resolved, has stabilised or is otherwise explained, is no longer of clinical concern, or the patient is lost to follow-up [REDACTED]

### 9.2 Time Period and Frequency for Collecting AE and SAE Information

All AEs and SAEs will be collected from signing of informed consent until the last follow-up visit at the time points specified in the SoA (Table 8-1).

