	
Part 2: Expansion Phase
 
Once the Recommended Therapeutic Dose has been determined in Part 1 (a), a minimum of 150 patients will be enrolled in to the Expansion Phase, which is split into 3 periods. For participants taking part in the Dose Finding Phase (Part 1), eligibility criteria will be reassessed prior to entering Part 2 of the trial.
 
1) Baseline visit
 
In a minimum of 50 participants the following will be performed:
 

• Administration of a test dose of RESP301, at the RTD

• Assesses response to RESP301 (incl. recording any AEs, FEV1 pre- and post dose and monitoring methaemoglobin levels pre-, during and post- administration, using fingertip sensor; methaemoglobin level should be <=2% before, <=5% during, and <=3% at 30-60 mins post dose (i.e. if still >3% at 30 mins, check again at 60mins post dose).

 
During the visit participants who satisfactorily tolerate the test dose will then be enrolled into the “dormant period” of the study for 12 months.
 
An independent Data Monitoring Committee will review the data from the 50 participants that received the RTD. Based on the data from these participants, it will be decided whether test doses should be administered to further participants before enrolling them into the Dormant Period.
 
2) Dormant Period
 
Dormant period patients are requested at the baseline visit, and monthly follow-up calls, to inform the study team if they develop exacerbation symptoms indicative of a respiratory infection. There will be no other study procedures or data collection during the “dormant study phase” unless the participant experiences exacerbation symptoms.
 
3) Treatment Period
 
A patient who experiences exacerbation symptoms for at least 24 hours should contact the study team as soon as practicable to allow a study interaction to be undertaken remotely (via video link, if possible), within 72 hours of onset of at least one of the following: fever (<math>>38.0^{\circ}\text{C}</math>), systemic malaise, increased cough or wheeze, increased sputum volume or increased purulence. During the remote visit the patient’s symptoms will be discussed and if

--	--

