## **Reporting of SAE**

### **SAE Reporting**

All SAEs will be recorded from signing of informed consent until the end of the study. Serious adverse events occurring after the end of the study and coming to the attention of the Investigator must be reported only if they are considered (in the opinion of the Investigator) causally related to study intervention.

Other events which must be reported in the same manner as an SAE include:

- Overdose (any dose above that specified in the protocol, not necessarily intentional)
- Abuse or misuse
- Medication error (any unintentional error in the dispensing or administration of an IMP)
- Occupational exposure (to a person other than the patient, for example spilling of IMP on hands of nurse or splashing in the eye)
- STIAMP (suspected transmission of an infectious agent via a medicinal product)

- Any AE that could be related to the protocol procedures and which could modify the conduct of the trial.

The Investigator must report any SAEs to the Sponsor **within 24 hours** of becoming aware of the event by emailing an SAE form to the Sponsor's PV department.

The Sponsor's PV department will confirm receipt within one business day. The site should re-send any report where acknowledgement of receipt is not provided.

Each episode of an SAE must be recorded on a separate SAE form. If new or amended information on a previously reported SAE becomes available, the Investigator should report this to the PV department on a new SAE form.

Where an SAE has not been reported to the Sponsor within the specified timelines, a reason for lateness must be included with the SAE form.

All SAEs will be recorded from signing of informed consent until the end of the study. Serious adverse events occurring after the end of the study and coming to the attention of the Investigator must be reported only if they are considered (in the opinion of the Investigator) causally related to study intervention.

- The primary mechanism for reporting an SAE will be using a paper SAE reporting form

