**Table 3: Schedule of Study Assessments (Part 2)**

Procedure	Screen 1	Screen 2/ Baseline Visit 	Dormant Period (monthly calls)	Pre-Treatment call (within 24-72 hrs of exacerbation onset)	Treatment Period (daily monitoring calls for 8 days)	Post Treatment Follow-up call (Day $14\pm 3$ PEoT)	Post Treatment Follow-up call (Day $28\pm 3$ PEoT)	Early withdrawal (Days 0, 14 or 28 $\pm$ 3)
Informed Consent	X	X						
Inclusion and Exclusion Criteria	X	X						
Demographics	X							
Medical History	X			X	X	X	X	X
Medication history and concomitant medications	X	X		X	X	X	X	X
Height, Weight and BMI	X							
Physical Examination 	X	X						
Pulmonary function test 	X	X						
Vital signs	X	X						
Methemoglobin level	X	X						
RESP301 administration 		X			X			
CCQ		X	X		X 	X		
Instructions of nebulizer		X		X	X			
Follow-up 			X					
Review of symptoms				X	X	X		
AE/SAE review	X	X			X	X	X	X
VAS 					X	X		

Body temperature 				X	X	X		
Treatment compliance					X			

 Patients who received a RTD test dose only and did not proceed to the dormant period, will receive a follow-up call on day 7±3 to discuss and record AEs.

 Only done if deemed necessary by the investigator

 Only done in patients who received a RTD test dose at the Baseline visit

 At baseline a single RTD dose for patients who were assigned to test dose and at the treatment period TID for 1- 7 days in patient with an exacerbation

 Done at Day 1 and Day 7

 Patients reminded to contact the study team if they experience exacerbation symptoms

 Daily during the treatment period, and if not recovered by end of treatment, continued until recovery or Day 14 post end of treatment

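### Part 2 participants who take a test dose and enter the dormant period have no scheduled adverse event enquiry after the baseline visit unless they exacerbate or withdraw, yet they count in the treatment-emergent AE percentages

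*Protocol*

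**What the plan says.** **Collection window.** Protocol 9.2 states: "All AEs and SAEs will be collected from signing of informed consent until the last follow-up visit". The sentence then ties collection to the schedule: "at the time points specified in the SoA (Table 8-1". Protocol Appendix 1, SAE Reporting, carries no such tie: "All SAEs will be recorded from signing of informed consent until the end of the study".

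**Schedule.** In SAP Table 3 the AE/SAE review row is marked at both screening/baseline visits, in the treatment period, at both post-treatment calls and at early withdrawal. It is blank for the monthly dormant calls and the pre-treatment call. Protocol Table 8-1 shows the same pattern for Part 2.

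**Content of the dormant calls.** Protocol 8.2 says that "the participants will receive monthly follow-up calls to remind them to contact the study team if they start experiencing exacerbation symptoms". SAP Table 3, footnote 6, says the same: "Patients reminded to contact the study team if they experience exacerbation symptoms". The synopsis, under Dormant Period, adds: "There will be no other study procedures or data collection during the" dormant phase, with an exception when exacerbation symptoms occur.

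**Follow-up after a single dose elsewhere.** Protocol 5.1 gives Part 1 participants a safety call on the morning of Day 2. For Part 2, SAP Table 3, footnote 1, says: "Patients who received a RTD test dose only and did not proceed to the dormant period, will receive a follow-up call on day 7±3", to record AEs. Protocol 8.1.6 also provides a call for this group.

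**Analysis.** SAP 5.11 tabulates every AE with onset after first administration and gives no closing date. SAP 5.2 puts anyone who inhaled any study medication in the safety set. SAP Table 1 gives Part 2 a single treatment label.

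**The concern.** The stated windows run to the last follow-up or the end of the study, but the schedule has no point in the dormant period, which lasts up to 12 months, at which anyone asks about AEs. A participant who tolerates the test dose, stays stable and never withdraws early has no AE review after baseline. The follow-up is also uneven: the participants judged tolerant in clinic are the ones with no later AE call.

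Two outputs are affected. Counts and cumulative incidence of AEs and SAEs are secondary endpoints in the protocol synopsis, and over dormancy they would rest on unsolicited reports. The SAP's Part 2 AE percentages would mix participants with one test dose and no later enquiry with participants asked daily through a treatment course.

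**Working it through.** No figure in the plan addresses this point, so there is none to reproduce. The check has two steps.

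**Step 1. Who is asked about AEs after a single dose**

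| Group | Next scheduled AE enquiry | Source |
|---|---|---|
| Part 1, any dose group | Day 2 call | Protocol 5.1, Table 8-1 |
| Part 2, test dose, does not proceed | Day 7±3 call | SAP Table 3 footnote 1 |
| Part 2, test dose, enters dormancy | None, unless treated for an exacerbation or withdrawn early | Table 8-1, SAP Table 3, Protocol 8.2 |

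The column headings of Protocol Table 8-1 are damaged in the text available, but the dormant cell is blank on either plausible alignment. SAP Table 3 is intact and also shows the pre-treatment call as blank.

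**Step 2. How many participants**

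Inputs:
- 50 test-dosed and 150 enrolled in Part 2 (SAP 4).
- 30 of 150 expected to exacerbate within 12 months (SAP 4).
- Exacerbation rates of 0.85 and 2.00 per person in the cited cohort study (Protocol 3.1). The text gives no time unit; I read them as annual.

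Assumptions: all 50 enter dormancy, everyone who exacerbates is treated, nobody withdraws early, no Part 1 participants carry over, and exacerbation is unrelated to having had a test dose.

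Plan's estimate:
- Share exacerbating: s = 30/150 = 20%.
- No later AE review: 50 × (1 − 0.20) = 40 participants.
- Time: 40 × 12 = 480 participant-months, or 40 person-years.

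Sensitivity, Poisson events with s = 1 − exp(−rate):
- Rate 0.85: s = 57.3%, and 50 × 0.427 = 21.4 participants.
- Rate 2.00: s = 86.5%, and 50 × 0.135 = 6.8 participants.

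If only 90% of the 50 tolerated the dose (an assumption), 45 would enter dormancy and the first figure becomes 45 × 0.80 = 36.

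Next, the weight of this group in the Part 2 safety set, if test dosing stops at 50. The set is then the 50 test-dosed plus the treated among the other 100, which is 50 + 100s.

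| s | No later AE review | Part 2 safety set | Share of denominator |
|---|---|---|---|
| 20% | 40 | 50 + 20 = 70 | 40/70 = 57% |
| 57.3% | 21.4 | 50 + 57.3 = 107.3 | 21.4/107.3 = 20% |
| 86.5% | 6.8 | 50 + 86.5 = 136.5 | 6.8/136.5 = 5% |

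The gap is present in every row; its weight depends strongly on the exacerbation rate.

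**The case against.** **Section 9.2 defers to the schedule.** Read in full, 9.2 does not contradict Table 8-1, and the synopsis sentence has its own exception for exacerbation symptoms. This stands: the plan does not forbid recording AEs in dormancy. What remains is a stated window with no enquiry inside its longest part, and an Appendix 1 SAE window without the schedule qualifier.

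**Events can still reach the database.** Protocol 9.1 relies on participant reports and makes investigators responsible for detecting events; 9.4 requires follow-up of those already reported. Dormant participants are told to report fever, malaise and worse cough, wheeze or sputum, and the pre-treatment call reviews symptoms, medication and medical history. A reader might infer that delayed AEs are systematically unobserved. The documents support only that they are not actively solicited.

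**The effect on the committee's decision is limited.** A reader might infer that the decision to drop the test dose rests on blind data. SAP 3.1 defines tolerability acutely: completing the dose, symptoms, methaemoglobin at 30 or 60 minutes, FEV1 at 60 minutes. Part 1 adds Day 2 calls after up to 4 × 8 = 32 planned administrations at or above the 4 ml RTD (SAP Table 1, groups 4 to 7). The committee charter is not available. The decision may lack information on later events, but its acute basis is intact.

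**All dormant time is too large a measure.** A reader might count 150 × 1 year = 150 person-years. If the test dose is dropped, about 100 of the 150 enter dormancy undosed. Their dormant events precede first dose and would only be listed (SAP 5.11).

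**Redaction.** Parts of Protocol 8.1.6 and some Table 8-1 notes are blacked out, so a post-test-dose contact there cannot be fully excluded. Protocol 8.2, the synopsis text and SAP Table 3 are readable and agree.

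**Conclusion.** The point holds for Part 2 participants who take a test dose and enter dormancy. In the readable text they have no scheduled AE enquiry after baseline unless they exacerbate or withdraw early, while both comparable single-dose groups get an AE call.

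About 40 of 50 participants (about 40 person-years) are affected on the SAP's own estimate, and about 21 to 7 if 57% to 86% exacerbate. These counts rest on all 50 entering dormancy, on no early withdrawals and, for the range, on annual Poisson rates. With an open-ended treatment-emergent rule and one Part 2 label, AE percentages are biased downward relative to a fully solicited population. The size of that bias cannot be computed, because the documents give no AE rates.

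This should be put right because the remedy is cheap. It does not undermine the acute tolerability assessment.

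**What to change.** **Protocol, if dormant follow-up is still running**
- Add AE/SAE review, including hospitalisation and death, to the monthly dormant call (at the least the first one after a test dose) and to the pre-treatment call, in Table 8-1 and SAP Table 3.
- Reconcile 9.2, Appendix 1, 8.2 and the synopsis sentence on data collection in dormancy.

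**SAP, in any case**
- Report Part 2 AEs by period, each with its own denominator: test dose to first monthly call; rest of dormancy; treatment to 28 days after end of treatment.

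**If dormant follow-up is over**
- This is possible, since SAP 5.1 cites a 2024 drug dictionary. Make the SAP change and state in the report that dormant-period events were only spontaneously reported.

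**Cost.** One question on calls already made, an eCRF page and a short amendment. The downside is more unrelated AEs to record. The SAP change alone costs some extra table columns.

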### 9.3 Method of Detecting AEs and SAEs

The method of recording, evaluating, and assessing causality of AEs and SAEs and the procedures for completing and transmitting SAE reports are provided in Appendix 1: Adverse Events: Definitions and Procedures for Recording, Evaluating, Follow-up, and Reporting.

### 9.4 Follow-up of AEs and SAEs

After the initial AE/SAE report, the Investigator is required to proactively follow each participant at subsequent visits/contacts. All SAEs will be followed until resolution,

stabilisation, until the event is otherwise explained, or the participant is lost to follow-up (as defined in Section [REDACTED])

Further information on follow-up procedures is given in Appendix 1: Adverse Events: Definitions and Procedures for Recording, Evaluating, Follow-up, and Reporting.

## **9.5 Regulatory Reporting Requirements for SAE**

Prompt notification (within 24 hours) by the Investigator to the Sponsor of an SAE is essential so that legal obligations and ethical responsibilities towards the safety of participants and the safety of a study intervention under clinical investigation are met.

The Sponsor has a legal responsibility to notify both the local regulatory authority and other regulatory agencies about the safety of a study intervention under clinical investigation. The Sponsor will comply with country-specific regulatory requirements relating to safety reporting to the regulatory authority, Institutional Review Board (IRB)/Independent Ethics Committee (IEC), and Investigators.

Investigator safety reports must be prepared for suspected unexpected serious adverse reactions (SUSARs) according to local regulatory requirements and Sponsor policy and forwarded to Investigators as necessary.

An Investigator who receives an Investigator safety report describing an SAE or other specific safety information (e.g., summary or listing of SAE) from the Sponsor will file it along with the Investigator's Brochure and will notify the local IRB/IEC, if appropriate according to local requirements..

## **9.6 Disease-Related Events and/or Disease-Related Outcomes Not Qualifying as AEs or SAEs (Not Applicable)**

## **9.7 Adverse Events of Special Interest (Not Applicable)**

No AEs of special interest are defined for this study.

## **9.8 Medical Device Deficiencies (Not Applicable)**

The medical device to be used in this study is a [REDACTED] nebuliser that is FDA-approved and CE-marked and is to be used per the manufacturer's recommendations. Therefore, data on device deficiencies will not be collected in this study.

## 10 Statistical Considerations

### 10.1 Statistical Hypothesis

Since this is an open label non-randomised study where the primary objective is to assess feasibility, no formal statistical analysis will be performed.

### 10.2 Sample Size Determination

The primary objective of this study is to determine [REDACTED]  
[REDACTED] and no formal sample size calculation was performed.

In Part 1, we aim to recruit [REDACTED] participants [REDACTED]

In Part 2, we aim to recruit 150 patients from secondary care and primary care sites in the UK into the dormant period. [REDACTED]  
[REDACTED]  
[REDACTED]  
[REDACTED]  
[REDACTED]  
[REDACTED]

### 10.3 Populations for Analyses

For purposes of analysis, the following analysis sets are defined:

**Table 10-1                   Populations for Analysis**

Population (Analysis Set)	Description
Intent-To-Treat (ITT) Population	The ITT Population will include all participants enrolled into the treatment period. Participants who withdraw from treatment early will be followed for the assessment of the Day 7 primary endpoint. All efficacy analyses will be performed using the ITT Population.
Per Protocol (PP) Population	The PP Population will include all participants in the ITT Population with no major protocol deviations that may significantly impact data integrity or patient safety. The PP Population will be used for supportive analyses of the efficacy measurements.
Safety Population (SP)	The SP will include all participants who inhale any amount of study intervention.

The ITT Population will be the primary analysis set for all efficacy analyses and the PP Population will be used to demonstrate robustness of results for the efficacy endpoint.

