## **4. SAMPLE SIZE JUSTIFICATION**

The primary objective of this study is to determine the MTD and RTD of RESP301 and to assess feasibility. No formal sample size calculation was performed. In Part 1, we aim to recruit up to 56 participants (8 per dose group) to receive one dose of RESP301 (alone or in combination).

In Part 2, we aim to recruit around 150 patients from secondary care and primary care sites in the UK into the dormant period. The first 50 consented participants will receive an initial test dose of RESP301 before progressing to the dormant period. If, based on the first 50 participants, the DMC determines that it is safe to do so, the remaining consenting participants will not be required to receive a test dose before progressing to the dormant period. It is estimated that over 12 months, 30 of the 150 enrolled participants will exacerbate. These participants will commence self-administered RESP301 treatment. Non-exacerbating participants will receive no further study interventions.

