## **5.2 Definition of Analysis Populations**

The following analysis sets will be identified prior to database lock, see section 10.3 of the protocol. Please note, that the FAS definition is slightly different from the ITT population in the protocol.

Screening	All patients who were screened (i.e. given informed consent)
Safety Set (SS)	All patients who inhaled at least one dose of (complete or partial) study medication. Subjects will be analyzed as treated.
Full Analysis Set (FAS)	All patients in the safety set (SS) who have at least one post treatment assessment.
Per-Protocol Set (PPS)	All patients in the FAS without a major protocol deviation that may significantly impact data integrity or patient safety.

The FAS set will be the primary analysis set for all efficacy analyses and the PPS set will be used to demonstrate robustness of results for the efficacy

endpoints. All other analyses will be based on the patients from the safety set.

All protocol violations/deviations will be reviewed and classified as either 'minor' (unlikely to appreciably affect trial outcomes) or 'major' (likely to affect outcomes) and this classification will be utilised to define the study populations for analysis purposes.

The assessment of major violations will be performed before the study database is locked and will be documented in the corresponding meeting/TC minutes. At a minimum the investigator, a sponsor representative and the CRA/monitor will participate in this review and will sign the meeting minutes.

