## **5.10 Analysis of Efficacy Variables**

All primary and secondary efficacy parameters, see section 3, will be summarized descriptively and no formal statistical analyses will be performed. The analyses will be performed by treatment group and overall, for both the FAS and PPS set using appropriate descriptive statistics. The results of the spirometry will also be presented over time, i.e. baseline, 30-, 60- and 90-minutes post baseline.

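### The SAP's Full Analysis Set departs from the protocol's ITT set in both directions: it admits people who never had a home course and drops treatment-period enrollees who never inhale

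*Protocol*

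**What the plan says.** Protocol 10.3 (Table 10-1) defines the efficacy set by entry to the treatment period: "The ITT Population will include all participants enrolled into the treatment period". It adds: "The ITT Population will be the primary analysis set for all efficacy analyses".

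SAP 5.2 starts from a Safety Set, "All patients who inhaled at least one dose of (complete or partial) study medication", and builds the FAS on it: "All patients in the safety set (SS) who have at least one post treatment assessment". The FAS takes over the ITT's role: "The FAS set will be the primary analysis set for all efficacy analyses". The Per-Protocol Set (PPS) is the FAS without major deviations. The only comment on the change is "Please note, that the FAS definition is slightly different from the ITT population in the protocol".

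Three other parts of the SAP determine what this does to the results:

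- **Presentation.** SAP 5.10 says "The analyses will be performed by treatment group and overall, for both the FAS and PPS set using appropriate descriptive statistics". SAP Table 1 has a single Part 2 group (RTD, N=150).
- **Never-dosed subjects.** SAP 5.1 treats anyone who received no study medication as a screening failure, lists them separately, and keeps them out of every table except disposition.
- **Endpoints.** SAP 3.1 gives three Part 2 primary endpoints. Commencement on the delivery day and receipt within 48 hours are defined among those who correctly reported an exacerbation. Compliance is defined among those who commence. The one secondary endpoint listed is test-dose tolerability in Parts 1(a), 1(b) and 2.

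**The concern.** The condition that defines the protocol's set, entry to the treatment period, is absent from the SAP's set. Two groups are then misplaced.

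- **(a) Let in.** Part 1 single-dose participants, and Part 2 participants who had only the clinic test dose, qualify for the FAS and PPS. They can have no home-course outcome. The single RTD group does not separate them from home-treated participants, and an overall column adds Part 1.
- **(b) Left out.** After the first 50, participants may enter the dormant period without a test dose. One who then reports an exacerbation, enters the treatment period and never inhales is in the protocol's ITT set, but not in the Safety Set and so not in the FAS. That person is a failure on the commencement endpoint, which is central to a feasibility study.

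At stake is the denominator of the descriptive percentages. With no formal testing planned, those percentages are the trial's feasibility and efficacy result.

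**Working it through.** **Does the FAS really include people with only a test dose?** The SAP does not define a post-treatment assessment. SAP 5.1 sets baseline as the last value before study drug, which points to any dose. The efficacy table list (SAP 15.2) puts the secondary endpoints and spirometry on the FAS/PPS, and the secondary endpoint is tolerability in Parts 1 and 2. The FAS must therefore contain these participants. Post-dose spirometry and the Part 1 Day 2 call mean that the assessment condition should remove few of them.

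**Inputs (SAP 4).** Up to 56 in Part 1; 150 in Part 2; first 50 test-dosed; 30 of 150 expected to exacerbate. Check: 7 groups × 8 = 56, which reproduces the SAP's figure, and 30/150 = 20%.

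**Assumptions.** All 30 enter the treatment period and inhale; everyone dosed has a later assessment; exacerbation is independent of test dosing.

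**(a) Part 2 FAS members with no home course**

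- Dosed = 50 + 100 × 0.20 = 70. No home course = 50 × 0.80 = 40. Share = 40/70 = 57%.
- All 30 exacerbators test-dosed: FAS 50, share 20/50 = 40%.
- None test-dosed: FAS 80, share 50/80 = 62.5%.
- All 150 test-dosed: share 120/150 = 80%.
- Protocol 3.1 cites 0.85 exacerbations per person in moderate COPD. If this is assumed to be per year and Poisson, 1 − exp(−0.85) = 57.3% exacerbate. Dosed = 50 + 57.3 = 107.3; no home course = 50 × 0.427 = 21.4; share about 20%.
- Break-even for a majority, with 50 test-dosed and E home-treated: 50 − E/3 = E, so E = 37.5.
- Overall column, with 56 distinct Part 1 people who do not enter Part 2: (40 + 56)/(70 + 56) = 96/126 = 76%. This is a ceiling for that scenario, because Part 1 participants may join several groups and may enter Part 2.

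**(b) Failures lost from the commencement endpoint** (assumed counts: 30 report and enter the treatment period, 27 commence on the delivery day, 3 never inhale)

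- Stated denominator: 27/30 = 90%.
- None of the 3 previously dosed: all leave the FAS, giving 27/27 = 100%.
- Test-dosed in proportion, 3 × 50/150 = 1: two leave, giving 27/28 = 96.4%.
- All 3 previously dosed: 27/30 = 90%, no bias.

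The bias is upward or nil. It vanishes if everyone is test-dosed, which is the setting where (a) is largest. For 48-hour receipt, the excluded person may have received the pack in time or not, so the direction is not fixed.

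**The case against.** A reader might infer that most of the FAS never started the home course and that the Part 2 primary percentages are therefore diluted. The documents do not support that.

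- **Primary endpoints.** They carry their own denominators. A test-dosed participant who never exacerbates is in none of them.
- **VAS.** SAP Table 3 schedules it only in the treatment period and follow-up, and SAP 5.1 leaves missing values missing. Test-dose-only participants contribute nothing.
- **Recovery and hospitalisation or death.** These are endpoints in the protocol synopsis, but SAP section 3 does not list them and the SAP table list does not name them. Dilution there is conditional on their being reported.
- **A majority.** It depends on about 30 home-treated. The synopsis calls 30 a minimum, and above about 37 the majority in Part 2 is lost.

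It is also fair that a broad set is needed for test-dose tolerability and spirometry, that the SAP discloses a difference, and that the study is single-arm and descriptive.

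All of this stands and limits (a). It does not answer (b). The stated denominators would include non-starters, but the SAP does not say how they combine with the FAS, and the SAP 5.1 rule removes never-dosed subjects from the tables. The patient listings of the primary endpoint are on the Safety Set too, so a reader could not restore the missing failures from them.

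**Conclusion.** The mismatch is real, and the SAP's description understates it. The two sets differ in both directions, and the PPS inherits both differences, so it is no robustness check on this point.

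The firmer consequence is (b): an upward bias in the primary commencement endpoint, and a possible effect on 48-hour receipt. Its size depends on how many enrollees without an earlier dose never inhale, which the documents do not predict. The 90% to 100% example rests on assumed counts.

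Consequence (a) is about 57% of Part 2 FAS members on the SAP's own estimate, ranging from about 20% to 80%. It matters only for home-course outcomes without a denominator of their own, such as recovery and hospitalisation or death if they are reported. It is not evidence that the primary endpoints or VAS are diluted.

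**What to change.** In SAP 5.2 and the sections that depend on it:

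1. Restore the protocol 10.3 set, all enrolled into the treatment period including those who never inhale, for home-course outcomes, and derive the PPS for those outcomes from it.
2. Keep each primary endpoint's stated denominator: everyone who correctly reported an exacerbation, dosed or not, for commencement and 48-hour receipt; commencers for compliance. The ITT count should not replace these.
3. Exempt these participants from the SAP 5.1 exclusion of never-dosed subjects.
4. Keep an all-dosed set for test-dose tolerability and spirometry.
5. Show no overall column across Parts 1 and 2 for home-course endpoints.
6. Replace the present remark on the FAS with a statement of the actual difference from the ITT set.

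The cost is SAP wording and one extra population flag, with no new data. The displayed N for home-course outcomes falls to about 30.
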